1.2. Statistical Hypotheses for Trial Objectives

The primary efficacy endpoint of this study is PFS. The null hypothesis is that there is no difference in PFS between daratumumab in combination with Rd and Rd alone in subjects with newly diagnosed multiple myeloma who are ineligible for high dose chemotherapy and autologous stem cell transplant.

The secondary endpoints such as ORR, VGPR or better rate, CR or better rate, MRD negativity rate, OS, TTP, PFS2, sCR rate, time to next treatment, time to response and duration of response will be evaluated as well.

1.3. Sample Size Determination

The sample size calculation is performed on the basis of the following assumption. Based on the published data, the median PFS for Rd arm is assumed to be approximately 24 months. Assuming the addition of daratumumab can reduce the risk of the disease progression or death by 25%, i.e., assuming the hazard ratio (DRd vs. Rd) of 0.75, a total of 390 PFS events is needed to achieve a power of 80% to detect this hazard ratio with a log-rank test (two-sided alpha is

0.05). With a 21-month accrual period and an additional 24-month follow-up, the total sample size needed for the study is approximately 730 (365/arm) subjects. The sample size calculation has taken into consideration an annual dropout rate of 5%.

Long-term survival follow-up will continue until 330 deaths have been observed or 7 years after the last subject is randomized, whichever is first. Therefore, this study will achieve approximately 80% power to detect a 27% reduction in the risk of death (hazard ratio = 0.73) with a log-rank test (two-sided alpha = 0.05) if 330 death events are observed at the study end.

1.4. Interim Analyses

Two interim analyses are planned. The first interim analysis, with a purpose to evaluate safety, has been performed after a total of approximately 100 subjects have been treated for at least 8 weeks or discontinued the study treatment. The second interim analysis will be performed when approximately 234 PFS events, which is 60% of the total planned events (390 PFS events), have been accumulated to evaluate the cumulative interim safety and efficacy of daratumumab in combination with Rd. The significance level at this interim analysis to establish the superiority of DRd over Rd with regard to PFS will be determined based on the observed number of PFS events at the interim analysis, using the O'Brien-Fleming boundaries as implemented by the Lan-DeMets alpha spending method. If the experimental arm (DRd) is numerically worse than the control arm in terms of PFS (observed hazard ratio >1 favoring the control arm), then the study may be terminated for futility.

More details about the conduct of these interim analyses can be found in a stand-alone IDMC charter.

2. GENERAL ANALYSIS DEFINITIONS

2.1. Visit Windows

For analyses of data by cycle, if data are collected by date (e.g., AE onset), the corresponding study evaluations will be assigned to actual sequential cycles, which are derived from the study treatment administration data. The start date of a particular cycle is defined as the date of the first scheduled dose of any component of the study treatment, and the end date of a cycle is the start date of the next cycle minus 1. For the last cycle, the end date is defined as the end of treatment visit date or the minimum of last study treatment date plus 30 days and subsequent antimyeloma therapy minus 1 day, if the end of treatment visit date is not available.

In general, if data (e.g., laboratory and vital sign etc.) are collected by cycle, the nominal cycle will be used to summarize data. However, due to possible cycle delays, assessment performed in the same cycle may not be well aligned in time scale for different subjects.

2.2. Pooling Algorithm for Analysis Centers

All participating centers in the study will be pooled together for analyses.

2.3. Study Treatment and Study Drug

In this study, study treatment refers to lenalidomide, dexamethasone, and/or daratumumab. Study drug refers to daratumumab.

2.4. Study Treatment Dosing Date

Study treatment dosing date is the date on which a subject actually receives study treatment (partial or complete) and will be recorded in the study treatment administration dataset.

For subjects who receive DRd treatment, the first study treatment date is defined as the earliest date of non-zero dose of the following administration: lenalidomide, dexamethasone or daratumumab. The last study treatment date is defined as the latest date of non-zero dose of the following administration: lenalidomide, dexamethasone or daratumumab.

For subjects who receive Rd treatment, the first study treatment date is defined as the earliest date of non-zero dose of the following administration: lenalidomide or dexamethasone. The last study treatment date is defined as the latest date of non-zero dose of the following administration: lenalidomide or dexamethasone.

2.5. Baseline Measurement

Baseline measurement is defined as the closest non-missing measurement taken on or prior to the first study treatment administration (including time if time is available, with exception of parameters associated with disease-related efficacy assessment such as SPEP, UPEP, kappa, lambda, kappa/lambda ratio, serum calcium, and albumin).

2.6. Unique Lab Value

In general, in instances when there are multiple records at a given visit date for lab parameters associated with disease assessment, the following rules will be applied to select the unique lab value for analysis: a) multiple records from both central and local lab, central lab value always takes precedence over local lab value; b) multiple records from central lab, select the latest value by time, visit number, or sequence number as the unique lab value; c) multiple records from local lab, select the latest lab value by time, visit number, or sequence number as the unique local lab value.

2.7. Imputation of Partial Dates

Unless specified otherwise, no data imputation will be applied for missing safety and efficacy evaluations. For analysis and reporting purpose, partial dates in adverse event (AE onset date; AE end date), concomitant therapies (start date; end date), MM diagnosis date, and start date of subsequent antimyeloma therapy will be imputed.

2.7.1. Missing/Partial Adverse Event Onset Date

If the onset date of an adverse event is missing completely or partially, the following imputation rules will be used.

- When month and year are present and the day is missing,
 - If the onset month and year are the same as the month and year of first study treatment, the day of first study treatment or the day-component of the AE end date (possibly imputed) is imputed, whichever is earlier
 - If the onset month and year are not the same as the month and year of first study treatment, then the first day of the month is imputed
- When only a year is present,
 - If the onset year is the same as the year of first study treatment. If AE end date is available and is prior to first study treatment, the day and month of AE end date are imputed. Otherwise, the day and month of first study treatment are imputed
 - If the onset year is different from the year of first study treatment, the 1st of January is imputed
- If the onset date is completely missing, the earlier one of the date of first study treatment and the AE end date is imputed as the onset date.

No imputation will be done for partial or missing AE onset time.

2.7.2. Missing/Partial Adverse Event End Date

If the end date of an adverse event is missing completely or partially, the following imputation rules will be used

- If month and year are present and the day of the month is missing, the last day of the month is imputed.
- If only a year is present, the 31st of December is used.
- If the imputed date is later than the date of death (if available), the date of death will be used as the imputed date instead.
- If the year of end date is missing, no imputation will be applied.

No imputation will be done for partial or missing AE end time.

2.7.3. Partial Concomitant Medication Start/End Date

In case of partially missing concomitant medication start/end dates, the following imputation rules will be applied. If the date is completely missing, no imputation will be performed.

- If only the day is missing, the 15th day of the month will be used
- If both the day and month are missing, the 30th of June will be used.

• If the medication was taken prior to study start, and the imputed start date is after first treatment date, further adjust of the imputed start date as the day prior to first dosing date; If the medication was taken after study start, and the imputed start date is prior to first dosing date, further adjust the imputed start date as first dosing date. Also adjust the imputed medication end date so that it is on or after first dosing date.

2.7.4. Partial Multiple Myeloma Diagnosis Date

For partial date of original multiple myeloma diagnosis, the following imputation rules will apply:

- If only the day is missing, set to 15th (as imputed date), and pick minimum of imputed date, date of collection and date of randomization
- If both the day and month are missing, set to January 1, and pick minimum of imputed date, date of collection and date of randomization
- If year is missing, no imputation will be applied.

If the imputed date of original diagnosis is after the randomization date, further adjust the imputed start date as the day before the randomization date.

2.7.5. Partial Subsequent Anticancer Therapy Start Date

If year or month of subsequent anticancer therapy start date is missing or no components of the start date are present, no imputation will be performed.

If only the day is missing, the following steps apply:

- If the month and year of the start date are the same as the month and year of last dosing date, the day of last dosing date or the day-component of the stop date of subsequent anticancer therapy is imputed, whichever is earlier.
- If the start month and year are not the same as the month and year of last dosing date, the first day of the month is imputed.

No imputation will be applied for missing or partial subsequent anticancer therapy end date.

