4.2.1. Definition

PFS is defined as the duration from the date of randomization to either progressive disease, according to the IMWG response criteria, or death, whichever occurs first. Subjects who start subsequent antimyeloma therapies for multiple myeloma without disease progression will be censored at the last disease assessment before the start of subsequent therapies. Subjects who withdrew consent from the study before disease progression will be censored at the last disease assessment before withdrawal of consent to study. Subjects who are lost to follow-up will be censored at the last disease assessment before subjects are lost to follow-up. Subjects who have not progressed and are still alive at the cutoff date for analysis will be censored at the last disease assessment. Subjects without any post-baseline disease assessment will be censored at the randomization.

Determination of dates of PFS event and dates for censoring is summarized in Table 2 as follows.

Table 2: PFS Event and Censoring Method

Situation	Date of Progression or Censoring	Outcome
Disease progression prior to start of	Earliest date that indicates disease progression	PFS event
subsequent antimyeloma therapy		
Death without subsequent antimyeloma	Date of death	PFS event
therapy		
No post-baseline disease assessment	Randomization	Censored
Other (e.g., withdrawal of consent to study	Date of last disease assessment prior to	Censored
participation, lost to follow-up, start of subsequent	withdrawal of consent to study participation, lost to	
antimyeloma therapy etc.)	follow-up, or subsequent antimyeloma treatment	
/	- · · ·	

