4.2.3.1. Progressive Disease Based on Investigator Assessment

A sensitivity analysis of PFS, in which progressive disease is based on investigator assessment according to the IMWG response criteria, will be performed in a similar manner as described in the Section 4.2.2.

The PFS definition used in the sensitivity analysis is similar to that defined in the Section 4.1.2, except for date of progressive disease and date of censoring. The date of progressive disease is the date of initial disease progression recorded in the Disease Progression CRF page or earliest date of confirmed progressive disease recorded in the Evaluation of Response CRF page, based on investigator assessment. Similarly, the censoring date is the latest date of disease response recorded in the Evaluation of Response CRF page, based on investigator assessment.

In addition, reasons for PFS and censoring based on investigator assessment will be summarized for ITT population.

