4.2.3.2. Not Censored for Start of Subsequent Anticancer Therapies

A sensitivity analysis of PFS derived from the algorithm by not censoring data due to start of subsequent anticancer therapies for subjects, who have not developed a confirmed progressive disease, will be performed in a similar manner as described in Section 4.2.2.

The PFS definition used in the sensitivity analysis is similar to that defined in Section 4.2.1, except for censoring data due to start of subsequent anticancer therapies. Subjects who start subsequent anticancer therapies for multiple myeloma without disease progression will NOT be censored at the last disease assessment before the start of subsequent therapies. If there is no confirmed progressive disease, the subjects will be censored at the last disease assessment before subjects are lost to follow-up or withdrawal of consent to study.

Determination of dates of PFS event and dates for censoring is summarized in Table 3 as follows

Table 3: PFS Event and Censoring Method

Situation	Date of Progression or Censoring	Outcome
Disease progression	Earliest date that indicates disease progression	PFS event
Death	Date of death	PFS event
No post-baseline disease assessment	Randomization	Censored
Other (e.g., withdrawal of consent to study participation, lost to follow-up, start of subsequent anticancer therapy etc.)	Date of last disease assessment	Censored

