4.3.6. Time to Disease Progression (TTP)

4.3.6.1. **Definition**

TTP is defined as the time between the date of randomization and the date of first documented evidence of confirmed PD, as defined in the IMWG response criteria, or death due to PD, whichever occurs first. Subjects who start subsequent antimyeloma therapies for multiple myeloma without disease progression will be censored at the last disease assessment before the start of subsequent therapies. Subjects who withdraw consent to study or are lost to follow-up or die without disease progression will be censored at the last disease assessment. Subjects who have not progressed at the cutoff date for analysis will be censored at the last disease assessment. Subjects without any post-baseline disease assessment will be censored at the randomization.

Determination of dates of TTP event and dates for censoring is summarized in Table 4 as follows.

Table 4: TTP Event and Censoring Method

Situation	Date of Progression or Censoring	Outcome
Disease progression prior to start of subsequent anticancer therapy	Earliest date that indicates disease progression	TTP event
Death due to disease progression prior to start of subsequent anticancer therapy	Date of death	TTP event
No post-baseline disease assessment	Randomization	Censored
Other (e.g., withdrawal of consent to study participation, lost to follow-up, start of subsequent anticancer therapy etc.)	Date of last disease assessment prior to subsequent anticancer treatment	Censored

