4.3.11. Duration of Response

4.3.11.1. Definition

Duration of response (DOR) is defined for subjects with a confirmed response (PR or better) as the time between first documentation of response and disease progression based on the computerized algorithm, according to IMWG response criteria, or death due to PD, whichever occurs first. Responders without disease progression will be censored at the censoring time point for TTP.

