1.2. Clarifications and Modifications

In order to allow these rules to be applied consistently and to be programmed, the Sponsor has added certain clarifications and modifications for using the IMWG criteria.

- **1.2.1.** Measurable disease is defined in the protocol by at least one of the following measurement: (1) serum M-protein $\geq 1 g/dL$ ($\geq 10 g/L$) or $\geq 0.5 g/dL$ ($\geq 5 g/L$) for subjects with IgA, IgD, IgE or IgM multiple myeloma; (2) urine M-protein ≥ 200 mg/24h; (3) serum FLC assay: involved FLC level ≥ 10 mg/dL (≥ 100 mg/L) provided serum FLC ratio is abnormal.
- **1.2.2.** The reference point for calculating increase and % of increase for M-protein, FLC and bone marrow plasma cells will be the lowest response value and the "lowest response value" does not need to be a confirmed value.
- **1.2.3.** Requires 2 consecutive (i.e., no intermediate values that do not meet the definition of PD) assessments made at any time before the institution of any new therapy (i.e., subsequent anti-cancer therapy). If a subject has an unconfirmed PD

followed by death due to PD within 30 days of unconfirmed PD, or PD (the same parameter as of initial observed PD) observed within 4 weeks after start of subsequent anti-cancer therapy, the unconfirmed PD will be considered as PD.

- **1.2.4.** If nadir serum M-protein is $\geq 50g/L$ ($\geq 5 \text{ g/dL}$), M-protein increases of $\geq 10g/L$ (1g/dL) is sufficient for progressive disease. It does not require meeting "increase of $\geq 25\%$ in the level of serum M-protein".
- **1.2.5.** Any 2 consecutive increase of serum M-protein \geq 5 g/L (\geq 0.5 g/dL) is consistent with progressive disease, assuming that increase of \geq 25% is met or not applicable, even if the serum M-protein level is below measurable disease threshold.
- **1.2.6.** The baseline value for assessing disease progression is the last pretreatment measurement (it applies to SPEP, UPEP, FLC, plasmacytomas and bone lesions except as noticed in Section 1.2.10). For example, if there is a screening value and a Cycle 1 Day 1 value (prior to start of treatment) for M-protein, the program ignores the screening value and uses Cycle 1 Day 1 as the reference point for assessing PD for the first post-treatment results.
- **1.2.7.** The program disregards serum M-protein and urine paraprotein measurements prior to Day 5 after dosing. These tests are considered too soon after dosing to be regarded as legitimate on-treatment values.

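### SAP 2.7.5 can impute a next-therapy start on or before a documented progression, and PFS, TTP and DOR then censor that progression: wrong as written, probably small in effect

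*SAP*

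**What the plan says.** SAP 2.7.5 covers a subsequent-therapy start date with only the day missing. If the start falls in the month of the last dose, "the day of last dosing date or the day-component of the stop date of subsequent anticancer therapy is imputed, whichever is earlier". A second branch applies otherwise: where the year and month of the start "are not the same as the month and year of last dosing date, the first day of the month is imputed". Neither branch refers to PD.

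The imputed date then decides event status:

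- **PFS (SAP 4.2.1, Table 2):** PD is an event only if it comes before next therapy. "Subjects who start subsequent antimyeloma therapies for multiple myeloma without disease progression will be censored at the last disease assessment before the start" of that therapy.
- **TTP (SAP 4.3.6.1, Table 4):** the event row is "Disease progression prior to start of subsequent anticancer therapy".
- **DOR (SAP 4.3.11.1):** "Responders without disease progression will be censored at the censoring time point for TTP".

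Protocol 8.4 sets the intended order: next therapy waits until PD is established by IMWG criteria. SAP 4.2.3.2 adds a PFS sensitivity analysis in which subjects starting new therapy without PD "will NOT be censored at the last disease assessment before the start of subsequent therapies". No such analysis is planned for TTP or DOR.

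Two related texts concern how PD is called. For ionised calcium, protocol 9.2.1.3 uses a value above the local upper limit of normal, and SAP Attachment 2, 1.2.14 uses a value above 1.5 mmol/L. For subjects with no baseline lesion data, Attachment 2, 1.2.10 takes the first post-treatment value as baseline, while 1.2.12 and 1.2.13 treat a later reported lesion as new.

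**The concern.** A date that nobody recorded can overrule a date that somebody did. If the imputed start lands on or before a documented PD, a real event becomes a censored observation, and the data set then shows an order of events that protocol 8.4 forbids.

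There are two separate faults. The first is a plain logic slip: the stop date enters only through its day number, so a stop months later can pull the start back before the last dose. The second is the absence of a bound. Elsewhere the SAP does bound imputed dates: at death (2.7.2), at first dosing (2.7.3) and at randomization (2.7.4). In 2.7.5 the date that decides event status has no such limit.

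The algorithm does not repair this. Attachment 2, 1.2.3 requires two consecutive "assessments made at any time before the institution of any new therapy". Its exceptions rescue an unconfirmed PD first seen before next therapy, not one first dated after the imputed start.

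The final CSR analysis will update efficacy (protocol 3.1). The documents do not say which derivation rules it will use; this SAP was written for Amendment INT-4.

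**Working it through.** The plan gives no figure for this rule, so the check applies 2.7.5 literally.

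**Worked cases** (PD and therapy start both in March, start day missing)

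| Case | Last dose | PD | Therapy stop | Imputed start |
|---|---|---|---|---|
| 1. Last dose in an earlier month | 25 Jan | 10 Mar | any | 1 Mar |
| 2. Last dose before PD, same month | 3 Mar | 10 Mar | none | 3 Mar |
| 3. Last dose after PD, stop in a later month | 20 Mar | 15 Mar | 5 Jun | 5 Mar |
| 4. Last dose after PD, no stop date | 15 Mar | 8 Mar | none | 15 Mar |

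The PD is lost in cases 1 to 3 and kept in case 4. If PD fell in a month before the therapy start, nothing is lost.

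**Counting day combinations.** Take a 31-day month with the true start after PD, and weight every combination equally. Let p be the PD day, l the last-dose day, s the true start day and d the stop day-number.

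- Case 1, p < s: C(31,2) = 465. The imputed day 1 is before PD in 435 and on the PD day in 30 (p = 1).
- Case 2, l < p < s: C(31,3) = 4,495. The imputed day is before PD in all.
- Case 4, p < l < s: 0 of 4,495 lost.
- Case 3, p < l < s with any d from 1 to 31: 31 × 4,495 = 139,345. The start is before PD when d < p, which is C(31,4) = 31,465, or 22.6%. It is on the PD day when d = p, which is 4,495, or 3.2%.
- Ignoring PD, the day-number comparison puts the start before the last dose in 465 of 31 × 31 = 961 pairs (48.4%).

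These counts describe the rule. They are not rates in the trial.

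**Who is exposed.** Protocol 10.2 has treatment stop for PD only after sponsor confirmation, so subjects treated until PD normally meet only case 3. Subjects who stop earlier for another reason continue disease evaluations and can meet cases 1 and 2.

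**Scale, on assumptions.** First the plan's own figure. Events = 4(1.960 + 0.842)² / (ln 0.75)² = 380 by Schoenfeld, against the stated 390. Power at 390 events is Φ(√390 × 0.2877/2 − 1.960) = 81.1%. Now let m be the share of PDs with a day-missing next-therapy start, and q the share of those lost. The documents give neither. A simulation assuming a mean PD-to-therapy lag of 14 to 42 days gave q of 7% to 33% when dosing ran past PD, and 29% to 60% when it stopped at or before PD. Events lost = 390 × m × q:

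| m | q = 10% | q = 60% | Power |
|---|---|---|---|
| 1% | 0.4 | 2.3 | 81.0% to 80.8% |
| 5% | 2.0 | 11.7 | 80.9% to 79.9% |
| 10% | 3.9 | 23.4 | 80.7% to 78.6% |

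**The bound at PD.** If the site PD date equals the algorithm date, or is later but still in that month, no PD is lost in cases 1 to 3. If the site date is 1, 3 or 7 days earlier, every case 1 and 2 PD is still lost and no case 3 PD is. If therapy truly began before PD in that month and nothing records it, the present rule makes no error (0 of 465; 0 of 4,960, which adds 465 combinations with start on the last-dose day to 4,495). The bounded rule counts all of them as events.

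**The case against.** The strongest reply has four parts.

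- **The counts for cases 1 and 2 hold by construction.** Day 1 cannot follow any PD in that month, and a last dose defined as earlier than PD stays earlier. This is right. A reader might take 465 of 465, or 22.6%, as the proportion of progressions lost; the documents support no such rate.
- **Imputing early is a trade-off, not simply an error.** SAP 4.2.1 and protocol 9.1.4 both foresee therapy started without documented PD, and for those subjects the present rule is correct. This stands. Bounding at PD reduces misclassification only if more than half of the affected subjects started after PD. Protocol 8.4 requires that of all subjects, but a requirement is not evidence about subjects with defective dates. The reply does not reach case 3, where comparing day numbers across months has no rationale.
- **The conditions are narrow.** Protocol 8.4 asks for therapy start and end dates, and missing days can be queried. PD is dated at its first qualifying test, while confirmation comes later, so PD and next therapy can readily fall in different months. This supports a small effect but does not justify the wording.
- **The consequences are limited.** SAP 4.2.3.2 covers PFS, TTP is outside the SAP testing hierarchy (protocol 11.3 does list it as a major secondary endpoint), and DOR has no formal comparison. All true.

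A reader might also infer that the lesion rules contradict each other outright. Attachment 2, 1.2.6 names 1.2.10 as an exception about the baseline value, and criteria e and f in 1.1.1 separate growth from new lesions, so the texts can largely be reconciled. What remains is an unwritten precedence and faulty cross-references: definite increase points to 1.2.8, a date rule, and new bone lesions point to 1.2.11, a plasmacytoma size rule.

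**Conclusion.** The point holds. SAP 2.7.5 is wrong as written in its stop-date comparison and incomplete in having no bound at a documented PD. Through Tables 2 and 4 it can turn a PD into censoring for PFS, TTP and DOR. It is worth correcting because the correction is cheap.

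The effect is probably small, but that is a judgement. Under the assumptions above, power changes by about one point at most if up to 5% of PDs have a day-missing therapy start. At 10% with a high loss share the change would be about 2.5 points. No direction by arm can be stated.

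A reader might infer that the established PFS superiority is in doubt. The documents do not support that: they give no count of affected subjects, and 4.2.3.2 already provides a PFS analysis that does not censor at next therapy.

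The ionised-calcium thresholds do conflict and must be reconciled; no view is taken here on which is right. Few subjects should be affected, since ionised calcium is used only when corrected calcium is unavailable and PD first met by hypercalcemia is reviewed clinically (1.2.16d). The lesion rules need clarification only.

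**What to change.** For analyses after the completed primary PFS analysis, amend SAP 2.7.5:

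1. Compare the full therapy stop date, not its day number.
2. Keep the imputed date inside the recorded start month and not after the full stop date. Within those limits:
   - impute no earlier than the last dose when it is in that month;
   - impute after a PD documented in that month, unless the record shows that therapy began first;
   - if PD is on the last day of the month, impute that day and count the PD as preceding therapy.

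   Take PD from the site record (SAP 4.2.3.1: "the date of initial disease progression recorded in the Disease Progression CRF page"), because algorithm confirmation itself depends on the next-therapy date.
3. Flag every subject whose PFS, TTP or DOR status depends on an imputed start, including those whose site and algorithm PD dates differ. Add a check of the 4.2.3.2 type for TTP and for DOR. Report later updates under both the present and the amended rule.

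In the worked cases the imputed start becomes 11 March (cases 1 and 2) and 20 March (case 3). A PD on 31 March gives 31 March, not 1 April. Therapy recorded in a month before the last dose stays in its month.

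The bound is not error-free. A subject who truly started therapy before PD in that month would count as an event. A PD can still be lost if the site date precedes the algorithm date or falls in the next month. The flag and the dual reporting are there for these subjects.

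Separately, the sponsor should reconcile protocol 9.2.1.3 with Attachment 2, 1.2.14, state how 1.2.10 relates to 1.2.12 and 1.2.13 when baseline lesion data are missing, and correct the cross-references in 1.1.1.

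Cost: a few SAP sentences, a small programming change, one flag variable and one added check each for TTP and DOR. No new data collection.
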